10.4 Appendix 4: Contraceptive guidance and collection of pregnancy information

Definitions

All study participants will be pregnant females (IC 3).

- The investigator will collect pregnancy information on any pregnant female participating in this study. The participant will be followed to determine the outcome of the pregnancy. The investigator will collect follow-up information on the participant and the neonate, and the information will be forwarded to the Sponsor. Generally, the follow-up will be at least 12 weeks after the delivery date. In certain circumstances, UCB may request that follow up is continued for a period longer than 12 weeks. Any termination of pregnancy will be reported, regardless of fetal status (presence or absence of anomalies) or indication for the procedure.
- While pregnancy itself is not considered to be an AE or SAE, any pregnancy complication or elective termination of a pregnancy will be reported as an AE or SAE. A spontaneous abortion is always considered to be an SAE and will be reported as such. Any post-study pregnancy related SAE considered reasonably related to CZP by the investigator will be reported to the Sponsor as described in Section 8.3.5. While the investigator is not obligated to actively seek this information in former study participants, he or she may learn of an SAE through spontaneous reporting.

Pregnancy and neonatal outcomes will be followed via Pregnancy Report and Outcome Forms which is the standard methodology for follow-up of all reported pregnancies and is a routine process unrelated to study procedure.

10.5 Appendix 5: Genetics

Not applicable.

This document cannot be used to support any marketing authorization application and any extensions or variations thereof.
PUBLIC COPY

10.6 Appendix 6: Liver safety – Suggested actions and follow-up assessments

No safety laboratory assessments will be performed in this study; as such, no evaluation of liver safety will be conducted.

This document cannot be used to support any marketing authorization application and any extensions or variations thereof.

PUBLIC COPY

**10.7 Appendix 7: Medical device incidents – Definition and
procedures for recording, evaluating, follow-up, and reporting**

Not applicable.

This document cannot be used to support any marketing authorization application and any extensions or variations thereof.
PUBLIC COPY

10.8 Appendix 8: Rapid alert procedures

Not applicable.

This document cannot be used to support any marketing authorization application and any extensions or variations thereof.
PUBLIC COPY

10.9 Appendix 9: Country-specific requirements

Not applicable.

This document cannot be used to support any marketing authorization application and any extensions or variations thereof.
PUBLIC COPY

10.10 Appendix 10: Abbreviations and trademarks

AE	adverse event
BCG	Bacillus Calmette–Guérin
BMI	body mass index
CI	confidence interval
CPMP	Committee for Proprietary Medicinal Products
CRO	contract research organization
CRP	C-reactive protein
CV	Coefficient of variation
CZP	certolizumab pegol
eCRF	electronic Case Report Form
ES	Enrolled Set
EWD	Early Withdrawal or Discontinuation
Fab	antibody fragment
GCP	Good Clinical Practice
HBsAg	Hepatitis B surface antigen
IB	Investigator's Brochure
IC	inclusion criterion
ICF	Informed Consent Form
ICH	International Council for Harmonisation
IEC	Independent Ethics Committee
IGRA	interferon gamma release assay
IMP	investigational medicinal product
IRB	Institutional Review Board
LLOQ	lower limit of quantification
MedDRA	Medical Dictionary for Regulatory Activities
NTM	nontuberculous mycobacterial
PK	pharmacokinetics
PK-PPS	Pharmacokinetic Per-Protocol Set
Q2W	every 2 weeks
Q4W	every 4 weeks
Q8W	every 8 weeks

RNA	ribonucleic acid
SAE	serious adverse event
SAP	Statistical Analysis Plan
SAS	statistical analysis system
SD	standard deviation
SFU	Safety Follow-up
SS	Safety Set
TB	tuberculosis
TEAE	treatment-emergent adverse event
TST	tuberculin skin test
ULN	upper limit of normal

This document cannot be used to support any marketing authorization application and any extensions or variations thereof.
PUBLIC COPY

10.11 Appendix 11: Protocol amendment history

The Protocol Amendment Summary of Changes Table for the current amendment is located directly before the Table of Contents.

Amendment 1 (Aug 29 2019)

This document cannot be used to support any marketing authorization application and any extensions or variations thereof.

PUBLIC COPY

Amendment 1 (29 Aug 2019)

Overall Rationale for the Amendment

The purpose of this substantial amendment is to implement pre-review feedback received from the Central IRB US (Advarra) dated 31 Jul 2019.

The first version of the protocol was not formally submitted.

Section # and Name	Description of Change	Brief Rationale
Title page	EudraCT number 2019-003410-13 has been added.	EudraCT number was omitted in original protocol.
Section 4.1	
Previous text:
 
This study is considered interventional due to the collection of blood samples from the women, which is not part of routine clinical practice. However, it is noninterventional regarding treatment with CZP and will only include pregnant women who decided with their treating physician to continue treatment with CZP prior to being recruited for and enrolled in the study. Study participants who start CZP treatment after confirmation of pregnancy will not be eligible to participate in the study. Study participants are responsible for procuring their own supply of commercial CZP as it is not provided as part of the study.
 
New text:
 
The study is interventional due to the additional collection of blood samples from women. However, all other study assessments are part of routine clinical practice (with the exception of the diary), and the decision to continue/discontinue CZP therapy during pregnancy will be made between the participant and her
	To clarify the text and to describe further that there is no intention to interfere with treating physician's decisions on the care of their patient

	treating physician, taking into account the potential risks to the mother and the benefits of CZP therapy, and according to the applicable local label.	
Section 6.5	Added text: Unless otherwise prohibited per protocol exclusion criteria, study participants are permitted to continue on their prescribed medical therapy for the disease in accordance with the instructions of their treating physician	To clarify the intention is for study participants to continue their prescribed therapy for their disease unless prohibited per protocol exclusion criteria.
Section 6.5.2	Section heading changed from: Prohibited concomitant treatments (medications and therapies) To: Concomitant medications that lead to study withdrawal	To further clarify that the intention is not to interfere with the physician's decision.
Section 6.5.2	Previous text: The study participant must not participate in any other interventional clinical study or receive any unauthorized medication throughout the Study Period. New text: The study participant must not participate in any other interventional clinical study or receive any unauthorized medication throughout the study period. Non-Interventional study (NIS) participation is allowed.	To allow for non-interventional study participation where applicable.
	Previous text: There are certain exclusion criteria and withdrawal criteria associated with	To further clarify that there is no intention to interfere with the treating physician's decision on treatment of their patient and to add

	
concomitant medication use; to protect the safety of the study participant and to ensure robust and interpretable data, there is no intention to interfere with the physician's decision on treatment.
 
The following concomitant medications are prohibited during the study:
 
New text:
 
There are no specific prohibited concomitant medications in this study, as it is not the intention to interfere with the physician's decision on treatment. However, there are certain exclusion criteria and withdrawal criteria associated with concomitant medication use to ensure robust and interpretable data. These criteria include:.
	language to describe that the use of any medications listed in section 6.5.2 would result in withdrawal from the study.
Section 7.2	
Previous text:
 
3. Participant takes prohibited concomitant medications as defined in this protocol (Section 6.5.2).
 
New Text:
 
3. Participant takes prohibited concomitant medications that lead to study withdrawal as defined in this protocol (Section 6.5.2).
	To align the withdrawal criteria with updates made in Section 6.5.2
Section 8	
Previous text:
 
Immediate safety concerns should be discussed with the sponsor immediately upon occurrence or awareness to determine if the participant should continue or discontinue CZP.
	To clarify it is the treating physician's responsibility to determine if the patient continues or discontinues treatment.

	
New text
 
It will be the responsibility of the treating physician to determine if the participant should continue or discontinue treatment. The sponsor should be informed immediately regarding safety concerns upon occurrence or awareness to determine if the participant should continue or discontinue participation in the study.
	
Section 8.3.5	
Previous text:
 
Women who become pregnant while taking CZP, and choose not to participate in the study, will still have their pregnancy followed per normal UCB guidance on pregnancy reporting.
 
New Text:
 
Information regarding collection of pregnancy-related data is located in Appendix 4 section 10.4
	To align text with Section 10.4
Section 8.5	
Previous text:
 
Excessive dosing (beyond that prescribed in the protocol and including overdose) should be recorded in the Drug Accountability module of the eCRF
 
New text:
 
Excessive dosing (beyond that prescribed per the local label) will be recorded by the study participant in the diary and also recorded in the eCRF. The dosing documentation will be reviewed and
	To clarify that dosing will be captured by the study participant in the diary and verified by the investigator and/or home health nurse in addition to documented in the eCRF.

	verified by the investigator and/or home health nurse	
	
Deleted text:
 
Decisions regarding dose interruptions or modifications will be made by the investigator in consultation with the Medical Monitor based on the clinical evaluation of the participant.
	To clarify that dosing decisions are the responsibility of the treating physician
Section 10.4	
Previous text:
 
Women who become pregnant while taking CZP, and choose not to participate in the study, will still have their pregnancy followed per normal UCB guidance on pregnancy reporting.
 
New text:
 
Pregnancy and neonatal outcomes will be followed via Pregnancy Report and Outcome Forms which is the standard methodology for follow-up of all reported pregnancies and is a routine process unrelated to study procedure.
	To clarify how pregnancy and neonatal outcomes will be followed-up.
Throughout	Change of "study treatment" to "CZP")	Deleted reference to 'study treatment' and clarified that this refers to CZP.

13.2.17 Anti-Drug Antibody Methods (Section 9.2.1, Section 9.2.2, and Section 9.2.3) ..	37
13.2.18 TEAE of interest (Section 11.3)	39
13.2.19 Identification of Opportunistic Infections (Section 11.3.1).....	39
STATISTICAL ANALYSIS PLAN SIGNATURE PAGE.....	41

LIST OF FIGURES

Figure 1-1: Study Diagram	10
---------------------------------	----

LIST OF ABBREVIATIONS

ADA	anti-CZP antibody
AE	adverse event
ASPS	All Study Participants Set
BLQ	below the limit of quantification
BMI	body mass index
CI	confidence interval
CSR	Clinical Study Report
CRF	Case Report Form
CRP	C-reactive protein
CSR	Clinical Study Report
CV	coefficient of variation
CZP	certolizumab pegol
DAP	Data Analysis Plan
DEM	Data Evaluation Meeting
eCRF	electronic Case Report Form
ES	Enrolled Set
FDA	Food and Drug Administration
HLT	Higher Level Term
ICC	Intraclass Correlation Coefficient
ICF	informed consent form
ICH	International Council for Harmonization
IVF	in vitro fertilization
LLOQ	lower limit of quantification
MedDRA	Medical Dictionary for Regulatory Activities
MRD	minimum required dilution
MSR	minimum significant ratio
OI	opportunistic infections
PD	Pharmacodynamics
PK	pharmacokinetic
PK-PPS	Pharmacokinetic Per Protocol Set
PT	preferred term
Q2W	every 2 weeks
Q4W	every 4 weeks
Q8W	every 8 weeks
SAE	serious adverse event
SAP	Statistical Analysis Plan
SAS	Statistical Analysis System
SD	standard deviation
SFU	Safety Follow-up

SMQ	standardized MedDRA query
SOC	system organ class
SS	Safety Set
TB	tuberculosis
TEAE	treatment-emergent adverse event
TFLs	Tables, Listings and Figures

This document cannot be used to support any marketing authorization application and any extensions or variations thereof.
PUBLIC COPY

1 INTRODUCTION

This statistical analysis plan (SAP) provides the necessary information to perform the final statistical analysis for study UP0085. It also defines the summary tables, figures and listings (TFLs) to be generated for the final clinical study report.

The SAP is based on the final Protocol Amendment 2 (30 AUG 2022). All references to study protocol hereafter refer to this version of the protocol, and, unless otherwise specified, the study will be analyzed as described in this version of the protocol. If a future protocol amendment necessitates a substantial change to the statistical analysis of the study data, or if analysis definitions must be modified or updated, this SAP will be amended accordingly.

The content of this SAP is compatible with the International Council for Harmonization (ICH)/Food and Drug Administration (FDA) E9 Guidance documents (Phillips et al, 2003).

The study assesses any changes in certolizumab pegol (CZP) plasma concentrations over the course of pregnancy, relative to the postpartum period. CZP is approved in adults for the treatment of chronic inflammatory diseases. It is valuable to evaluate whether the physiologic changes underlying pregnancy impact the pharmacokinetic (PK) profile of CZP during pregnancy in order to ensure that women who require CZP treatment during pregnancy are able to achieve therapeutic steady state levels of CZP.

Revision(s) of this SAP will not be required for any subsequent amendments to the protocol which do not change the analyses described in this SAP.

2 PROTOCOL SUMMARY

2.1 Study objectives

2.1.1 Primary objective

To assess systemic CZP exposure across the course of pregnancy in study participants with chronic inflammatory diseases

2.1.2 Secondary objectives

- To assess the formation of anti-CZP antibodies (ADA) across the course of pregnancy
- To assess the safety of CZP in study participants with chronic inflammatory diseases across the course of pregnancy

2.1.3 Other objectives

- To assess changes in body mass index (BMI), C-reactive protein (CRP) and albumin across the course of pregnancy

2.2 Study variables

2.2.1 Primary Outcome variable

Predose and postdose plasma CZP concentrations in women during pregnancy, relative to postpartum

2.2.1.1 Secondary Outcome variables

- Plasma levels of ADA throughout the study period
- Treatment-emergent adverse events from time of informed consent through Safety Follow-up (SFU)
- Pregnancy outcome

2.2.1.2 Other Outcome variables

- BMI
- CRP levels
- Albumin levels

2.3 Study design and conduct

This is a Phase 1B, multicenter, longitudinal, interventional, prospective, PK, open-label study evaluating the impact of pregnancy on the PK of CZP. The study will recruit women who are already on prescribed commercial CZP with both a dosing regimen selected with guidance from the participant's treating physician and an indication approved for use in their country, and who become pregnant and continue treatment with CZP. A postpartum predose blood sample taken 12 weeks (± 1 week) after delivery, once the mother is considered to have returned to a pre-pregnancy physiological state, will serve as a within-participant reference sample. If possible, a postdose sample will be taken 1 week (± 1 day) after the 12-week postpartum dose.

This study is considered interventional due to the collection of blood samples from the women, which is not part of routine clinical practice. However, it is noninterventional regarding treatment with CZP and will only include pregnant women who decided with their treating physician to continue treatment with CZP prior to being recruited for and enrolled in the study.

The study consists of a Screening Period, Sampling Period (consisting of a Pregnancy Period and Postpartum Period), and SFU contact, as shown in [Figure 1-1](#) and described below.

The full Schedule of Activities is provided in the protocol (Table 1-1).

- **Screening Period:**

Women of childbearing potential already on commercial CZP can register to indicate interest in the current study. After confirmation of pregnancy, the women will consent to participate in the study and will be eligible to enroll once CZP levels have reached steady state.

Confirmation of steady state is based on participant records and/or reports from the prescribing physician indicating that the participant has taken CZP for at least 12 weeks at the same dosing regimen prior to the Enrollment Visit, which must take place at ≤ 10 weeks gestational age.

- **Sampling Period:**

- **Pregnancy Period:**

PK samples will be collected prior to the subsequent dose (predose) every 4 weeks (Q4W) starting with the first dose after enrollment. Further, postdose (7 ± 1 day after dose administration) PK samples will be collected every 8 weeks (Q8W) throughout the

pregnancy. It is expected that there will be approximately 6 predose and 3 postdose PK samples collected per study participant (if there are no discontinuations) over the pregnancy.

– **Postpartum Period:**

A predose sample 12 weeks (± 1 week) postpartum will be collected during the Postpartum Period. If possible, 1 additional postdose sample 1 week (± 1 day) after the 12 weeks postpartum dose will also be collected.

• **Safety Follow-up contact:**

All study participants will be contacted via telephone for a SFU 5 weeks (± 5 days) after final study visit.

If any participant withdraws early, she will complete the SFU contact.

The end of the study is defined as the date of the SFU/last contact of the last participant in the study.

Number of participants:

Approximately 25 to 30 participants are planned to be screened to achieve approximately 20 enrolled study participants (i.e., study participants who have provided the first blood sample). Enrollment will occur until a minimum of 10 study participants have longitudinal data (defined as at least 4 quantifiable predose and 2 quantifiable postdose PK samples during pregnancy and at least 1 quantifiable postpartum sample) over the study period.

Treatment groups and duration:

[figure not shown]
This study will include pregnant women who have decided to continue treatment with commercial CZP in accordance with their treating physician prior to participating in the study. Study participants will be responsible for obtaining and administering commercially available CZP under the care of their physician and according to the locally approved product label.

The total study duration for a study participant will be a maximum of 53 weeks (40 weeks gestation period and up to 13 weeks (± 3 days) postpartum).

2.3.1 Schema

A schematic of the study design is provided in [Figure 1-1](#).

Figure 1-1: Study Diagram

CZP=certolizumab pegol; PK=pharmacokinetics; Q2W=every 2 weeks; Q4W=every 4 weeks

^a CZP dosing for at least 12 weeks before enrollment

^b First CZP dose post-enrollment

^c Timing and the number of visits across the pregnancy will vary for individual study participants

2.4 Determination of sample size

Because no formal hypothesis testing will be conducted, the sample size of 15 study participants is deemed sufficient for a small exploratory Phase 1B study. It is expected that up to 25 to 30 women will need to be screened to ensure that approximately 20 study participants are enrolled, in order to allow for approximately 15 evaluable study participants. These 15 evaluable participants are expected to provide the minimum of 10 study participants providing longitudinal data (defined as at least 4 quantifiable predose and 2 quantifiable postdose PK samples during pregnancy and at least 1 quantifiable postpartum sample) over the study period.

3 DATA ANALYSIS CONSIDERATIONS

3.1 General presentation of summaries and analyses

Statistical analysis and generation of tables, figures, study participant data listings, and statistical output will be performed using SAS® Version 9.3 or higher. All tables and listings will use Courier New font size 9.

Descriptive statistics will be displayed to provide an overview of the study results.

For categorical parameters, the number and percentage of study participants in each category will be presented. Unless otherwise noted, the denominator for percentages will be based on the number of study participants included in the respective analysis set. Study participants with missing PK/ADA data will be addressed in [Section 4.2.3](#). Other missing data can generally be accounted for using one of the following approaches:

- Percentages will be summarized based on all study participants in the analysis set and a “Missing” category (corresponding to study participants with missing data for the variable being summarized) will be included as the last row in the list of categories being summarized.
- Percentages will be based only on those study participants with observed data for the variable being summarized. As the denominator may be different from the number of study participants in the analysis set being considered, the denominator should be displayed in the table. The general format for displaying this will be “n/Nsub (%)”, where n=number participants in a category and Nsub=total number of participants with observed data.

The approach to be considered will be further specified in the relevant section of the variable of interest.

Unless otherwise noted, all percentages will be displayed to one decimal place. No percentage will be displayed for zero counts, and no decimal place will be presented when the percentage is 100%.

Unless stated otherwise, continuous endpoints will be summarized by timepoints.

For continuous parameters, descriptive statistics will include number of study participants with available measurements (n), arithmetic mean, standard deviation (SD), median, minimum, and maximum (unless otherwise stated). If n=3, only n, mean, median, minimum and maximum will be displayed. If n<3, only n, minimum and maximum will be displayed. For both cases, any summary statistics that are not displayed will be replaced with ‘NA’ and explained in a footnote.

Decimal places for descriptive statistics will always apply the following rules:

- “n” will be an integer.
- Mean, SD, and median will use 1 additional decimal place compared to the original raw value from the Case Report Form (CRF).
- Coefficient of variance (CV [%]) will be presented with 1 decimal place.
- Minimum and maximum will have the same number of decimal places as the original raw value.

If the number of decimal places reported in the raw data is varied then either the maximum raw number of reported decimal places or 3 will be used, whichever is the lowest, as a guide for the descriptive statistics.

Unless stated otherwise, statistical tests will be performed 2-sided and p-values will be rounded to 4 decimal places. P-values less than 0.0001 will be presented as “<0.0001” and p-values greater than 0.9999 will be presented as “>0.9999.” Statistical comparison will be performed at the 0.05 level of significance.

The SAS® outputs supportive of any statistical model (i.e., all excluding the descriptive analyses) will be provided as a separate PDF document in addition to TFLs. These outputs will be included in the ‘Documentation of Statistical Methods’ section of the clinical study report.

The abbreviation for certolizumab pegol is CZP and will be used in tables and listings headers. Unless otherwise specified, in the TFLs study participants on Certolizumab pegol will be displayed in columns by dosing regimen and all study participants as:

- “Not Dosed”
- “CZP 200mg Q2W”
- “CZP 400mg Q2W”
- “CZP 400mg Q4W”
- “All Dosed Participants”

An additional “Other” category will be added to the tables in case there are dosing regimens outside those listed. The “Not Dosed” category includes participants who enrolled but did not record a CZP dose relative to any PK samples prior to discontinuation. The “All Dosed Participants” category includes participants in CZP 200mg Q2W, CZP 400mg Q2W and CZP 400mg Q4W combined.

Study Participants will be grouped according to the commercial CZP dosing regimen that was in effect at enrollment (actual dose). Any participant with a dose reduction or increase will be summarized in the initial dosing regimen group.

All repeated and unscheduled measurements will be presented in the data listings, where applicable. The following general rules will apply to all repeated and unscheduled measurements:

- Unscheduled measurements will not be used in the descriptive statistics.
- For repeated measurements only the scheduled latest value can be used in the calculation of the descriptive statistics.

Unless otherwise stated, listings will be sorted by dosing regimen, study participant number, variable (if applicable) and visit (if applicable, including timing relative to dosing if applicable). All listings will include repeat and unscheduled measurements; such measurements will appear in chronological order together with the scheduled visits, i.e., a repeated measurement will appear directly after the visit and time relative to dosing for which the repeat measurement was performed. In all the listings dates will be presented in the format ‘YYYY-MM-DD’ and times will be presented in 24h clock format as ‘hh:mm’.

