3.6 Treatment assignment and treatment groups

The study will include pregnant women who have decided to continue treatment with commercial CZP in accordance with their treating physician prior to participating in the study. The commercially approved dosing regimens (200mg Q2W or 400mg Q2W or 400mg Q4W) will be permitted following the guidance of each study participant's physician.

After enrolment into the study, the study participant's physician may modify the dosing regimen as necessary. In such cases, non-approved CZP dosing regimens will also be allowed, at the discretion of the study participant's physician and in a manner independent of this study, as long as the regimen does not exceed 400mg Q2W and the dose is recorded in the diary. All dosing regimens outside the commercially approved will be categorized as other.

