13.1.4 Definition of past and prior medications (Section 6.5)

- Past medications are those that are ongoing at the time of first day of the last menstrual period and those that started after the first day of the last menstrual period and stopped prior to entering the screening period.
- Prior medications are those that are ongoing at the time of first day of the last menstrual period and those that started after the first day of the last menstrual period prior to entering the screening period.
- Concomitant medications are medications with at least 1 day in common with the screening period or sampling periods.
- Prior medications may include both past medications and concomitant medications.

13.1.5 **Exclusion of TEAE tables (Section 11.3)**

For the following AEs of interest, no additional tables will be provided, as these are included in the standard AE summaries:

- Congestive heart failure
- Lupus and lupus-like syndrome
- Serious skin reactions (e.g., Stevens Johnson Syndrome, toxic epidermal necrosis, and erythema multiforme).

This document cannot be used to support any marketing application and any extensions or variations thereof.
PUBLIC COPY

13.2 AMENDMENT 2

Rationale for the amendment

The major purpose of this SAP amendment was to align text with protocol amendment 2 and with more recent standards, and to make further clarifications for programming.

The main SAP amendments can be summarized as follows:

- Change of sample size text to reflect the minimum required number of participants
- Inclusion of a Not Dosed group for the participant who withdrew from the study prior to dosing during the pregnancy period and change from 'All Participants' to 'All Dosed Participants' to avoid counting this participant twice.
- Clarification of the calculation of geometric CI and ICC
- Clarification of the definition of gestational week
- Rewording of the reference point for plasma concentration
- Updated the definitions of the ES, SS and PK-PPS
- Handling of missing dates for imputation rules
- Addition of a section to describe the summary of medical conditions leading to CZP use along with dictionary terms to use for identifying the medical conditions.
- Clarification of which PK graphs will be produced
- Details of anti-drug antibody status and classification definitions and summaries
- Addition of a listing to display infant illnesses
- Cosmetic and grammatical corrections
- Addition of a section for the identification of opportunistic infections

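### The SAP's 'All Dosed Participants' column omits the 'Other' regimen group, and SAP Sections 3.1 and 3.6 leave open who belongs in 'Other'

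*SAP*

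**What the plan says.** SAP Section 3.1 sets the default table layout. It says that participants "will be displayed in columns by dosing regimen and all study participants as" a list of five labels: 'Not Dosed', the three named regimens (200mg Q2W, 400mg Q2W, 400mg Q4W) and 'All Dosed Participants'. It then provides that an 'Other' "category will be added to the tables in case there are dosing regimens outside those listed". In the same paragraph the overall column is defined: it "includes participants in CZP 200mg Q2W, CZP 400mg Q2W and CZP 400mg Q4W combined". 'Other' is not part of that sum.

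Section 3.1 also fixes the time of classification. Participants are grouped by the regimen they were on at enrolment, and "Any participant with a dose reduction or increase will be summarized in the initial dosing regimen group".

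SAP Section 3.6 deals with changes made after enrolment. It says that "non-approved CZP dosing regimens will also be allowed, at the discretion of the study participant's physician", up to a stated cap and if recorded in the diary. The sentence directly after that reads: "All dosing regimens outside the commercially approved will be categorized as other". It does not refer back to the enrolment rule in Section 3.1.

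The rationale for SAP Amendment 2 (Section 13.2) explains the label of the overall column as a "change from 'All Participants' to 'All Dosed Participants' to avoid counting this participant twice", where the participant meant is one who withdrew before dosing in the pregnancy period.

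**The concern.** There are two linked problems. First, a column labelled as all dosed women is defined so that it leaves out a group of dosed women. 'Not Dosed' is a separate column, so anyone in 'Other' has been dosed. The amendment rationale gives a reason for keeping the Not Dosed participant out of the total, but none for keeping 'Other' out, so the omission looks unintended.

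Second, a woman who enrols on a named regimen and later moves to a non-approved one stays in her initial group under Section 3.1, yet can be read into 'Other' under Section 3.6. Two programmers could place her differently, and the overall column would change with the choice.

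At stake is the overall column of the default summary tables, chiefly the adverse event tables of SAP Section 11.3. In a study of this size, one woman more or less is visible in that column.

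**Working it through.** No figure in the plan can be reproduced here. The sample size is not derived from a formula, and the documents do not say how many women are in 'Other'. The check is a comparison of the two rules, followed by simple counts.

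**Inputs.** About 20 enrolled and about 15 evaluable participants (SAP Section 2.4). Column definitions and the enrolment rule (SAP Section 3.1). The rule on non-approved regimens (SAP Section 3.6). Regimens eligible at entry (Protocol Section 4.2), which are the three that SAP Section 3.1 names.

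**Step 1: where each woman falls.**

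| Dosed woman | SAP 3.1 | In the total? | SAP 3.6 read alone | In the total? |
|---|---|---|---|---|
| Same named regimen throughout | Named group | Yes | Named group | Yes |
| Switches between named regimens | Initial group | Yes | Not 'Other' | Yes |
| Enrols on a named regimen, moves to a non-approved one | Initial group | Yes | 'Other' | No |
| Enrols on an unlisted, non-approved regimen | 'Other' | No | 'Other' | No |

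The sections diverge only in the third row. The fourth row is lost from the total under either section, but Protocol Section 4.2 does not foresee it.

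**Step 2: size.** Let N be the number of dosed women and k the number in 'Other'. As written, the overall column holds N − k; with 'Other' included it holds N. The share omitted is k/N. Since k is unknown, 0 to 3 is assumed.

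| k | N = 20: column, share omitted | N = 15: column, share omitted |
|---|---|---|
| 0 | 20, 0% | 15, 0% |
| 1 | 19, 5.0% | 14, 6.7% |
| 2 | 18, 10.0% | 13, 13.3% |
| 3 | 17, 15.0% | 12, 20.0% |

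The 20 and 15 are planning numbers treated as if all were dosed. If one of 20 were in 'Not Dosed', each woman in 'Other' would count for 1/19 = 5.3%, which lies inside the same range.

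**Step 3: effect on a percentage (assumed example).** Suppose an adverse event occurs in 5 of 20 dosed women: 5/20 = 25.0%. If 2 of those 5 are in 'Other', the overall column shows (5 − 2)/(20 − 2) = 3/18 = 16.7%. Section 3.1 takes the analysis set as the default denominator. If that were applied to the three-regimen numerator, the result would be 3/20 = 15.0%. If the 2 women in 'Other' had no event, the column would show 5/18 = 27.8%, so the direction is not fixed.

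**Step 4: continuous variables.** Section 3.1 shows only n, minimum and maximum when n is below 3. With one or two women in 'Other', that column would show no mean or median, and those women would not enter the overall mean either.

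**The case against.** The strongest reply is that the two sections can be read together. Section 3.6 labels regimens: it says what counts as 'Other'. Section 3.1 assigns participants: it says when a woman is classified, and it has an express rule for dose changes. On that reading nobody changes column after enrolment. Because the regimens eligible under Protocol Section 4.2 are the three named ones, and inclusion criterion 4 requires a stable maintenance dose for at least 12 weeks, 'Other' should then be empty and the total complete.

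Much of this stands. The two sections are in tension rather than in flat contradiction, and an empty 'Other' is the natural expectation under Section 3.1. What remains is that Section 3.6 puts its sentence directly after the text on post-enrolment changes without deferring to Section 3.1, and that the definition of the total is incomplete whenever the 'Other' column is used.

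A reader might infer three stronger things, none of which the documents support:

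- **That any woman whose regimen is modified drops out of the total.** Section 3.6 concerns only regimens outside the approved ones, so a switch among the three named regimens leaves her in the total under either section.
- **That such women disappear from the overall results.** They keep their own column, stay in the listings, and stay in the primary mixed model, which is fitted on the PK-PPS with no regimen term or regimen-based exclusion (SAP Sections 9.1.1 and 9.1.2). The descriptive PK summaries are specified by regimen (Section 9.1.3), so the overall column is not their main vehicle.
- **That the overall column is biased.** Women moved to a non-approved regimen may differ from the rest, but neither their number nor the direction of any shift can be known from the documents.

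**Conclusion.** The point holds as a reporting defect of minor weight. As written, the overall column is wrong whenever 'Other' contains anyone, and the SAP does not say unambiguously who belongs there. Each woman placed in 'Other' takes 5% to 6.7% off the overall column at the planned 20 or 15 participants. Losses of 15% to 20% would need three such women, which is an assumption and not a forecast. If 'Other' is empty, nothing changes. The primary PK estimate is untouched in every case. The conclusion concerns table groups only and passes no judgement on any dosing rule.

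**What to change.** Two edits, with no new data and no change to the models:

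1. In SAP Section 3.1, define 'All Dosed Participants' as the three named regimens plus 'Other', that is, everyone in the analysis set who is not in 'Not Dosed'.
2. In SAP Section 3.6, state that table grouping, including assignment to 'Other', follows the regimen in effect at enrolment, so that it agrees with Section 3.1.

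The total should not be defined as women with at least one recorded CZP dose. Section 3.1 defines 'Not Dosed' by the absence of a dose recorded relative to PK samples, while Protocol Table 1-1 records commercial CZP treatment from Screening. A 'Not Dosed' participant could therefore have a recorded dose and be counted in both columns, which is the double count that Amendment 2 set out to avoid.

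The cost is one clause in each section and the matching line in the table specifications.
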